refraining from food, beverages (with the exception of water), alcohol and caffeine. Before any data collection, participants provide written informed consent and complete a HIPAA authorization form in accordance with our IRB policy. At this visit, weight and height will be measured to calculate BMI. Individuals who meet the BMI criteria will undergo a medical history and a cognitive test (MoCA). The medical history (including blood pressure, review of medications, and a fasting blood draw for metabolic panel, vitamin D level, and blood cell count) will exclude those with recent history of coronary heart disease, cancer, liver or renal disease, severe pulmonary disease, gross physical impairment, uncontrolled hypertension, or any contraindications to exercise. The fasting blood profile will exclude those with uncontrolled diabetes,⁶⁹ anemia, or liver, renal, or hematological dysfunction. Individuals with abnormal results at screening will be referred to their physicians. Prior to randomization, eligible participants will be asked if they would like to participate in an MRI ancillary study. This is visit 2.1 listed in the table on page 7. Refusal to participate in the ancillary study will not exclude them from the main (parent) study. See Appendix A for details of the MRI ancillary study. Eligible participants will be randomized to treatment using a web-based randomization scheme developed by the biostatistician, stratified by sex with random block sizes.

Study Interventions

Weight Loss intervention: 9-mo WL phase—All participants will undergo a dietary WL intervention designed to elicit behavioral changes leading to decreased caloric intake sufficient to yield a ~10% loss of initial body mass. The WL intervention includes nutrition education, state-of-the-art behavioral methods for promoting WL, and strategies that optimize self-regulation.^{8, 70, 71} During the intensive phase of WL (months 1-6), participants will meet in weekly group sessions delivered by either the RD or staff trained on specific elements of the intervention with individual sessions possible on an as needed basis. These group meetings will transition to bimonthly group meetings during months 7-9 and to monthly follow-up phone/email contact during the follow-up phase (months 10-18).

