The Fitbit and website are used to induce behavior change over the course of the intervention; participants begin wearing the Fitbit daily for the first 9 months and then wear time is tailored to each individual for the remainder of the study, however, we ask that all participants use the devices at least 2 days each week as described above.

The SitLess intervention counseling sessions occur in conjunction with the WL sessions and follow the same contact schedule to achieve treatment goals. Participants meet weekly during the first 6 months and bimonthly during months 7-9. These sessions will focus on: (1) reviewing data from the activity monitors, (2) reinforcement for observed changes in behavior, and (3) motivational interviewing and problem solving to increase commitment to change and assist with overcoming barriers.⁷³ The goal is to build commitment to the use of the devices and to link the feedback to improvements in personally-valued outcomes in their daily lives.

9-mo Follow-up phase—During this phase, participants will receive a monthly phone call or email contact for the purpose of emphasizing adherence to the SitLess goals and the Fitbit activity tracking and associated website.

Aerobic exercise intervention: 9-mo WL phase—Participants in the WL+EX and WL+EX+SitLess treatment arms will be asked to perform structured aerobic exercise (mostly treadmill walking) of moderate-intensity for 4-5 days/week, progressing to a duration of 200

min/week. Participants will attend center-based sessions for at least 3 days/week during the first intensive 6-month phase and at least one day/week during the second 3-month transition phase (months 7-9), with recording of home-based exercise for the other 2-4 days/week. The rationale for, background education on exercise training, and monitoring of study progress occurs in conjunction with the WL sessions in a manner consistent with the SitLess intervention. The level of exercise is based on current public health recommendations from the American Heart Association and American College of Sports Medicine (ACSM) for optimizing cardiovascular fitness in older adults,⁷⁴ and the ACSM recommendation for appropriate physical activity strategies for WL.⁷⁵

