The supervised exercise sessions will take place in our research facility on motorized treadmills under the direction of an exercise interventionist. Participants will keep a log of their treadmill speed, grade, exercise duration, and the amount of energy expended for each exercise session which is used for feedback and reinforcement. All participants will be instructed to wear proper footwear, will be familiarized with the treadmills prior to use and will be instructed in fall prevention safety. Participants will warm-up by walking for 3-5 min at a slow pace and will then walk at an intensity of 65-70% of heart rate reserve (HRR, assessed during the VO₂peak test). In general, the duration of supervised walking exercise will progress from 15-20 min at 50% HRR the 1st week to 40-50 min at 65-70% HRR by the end of the 6th week and thereafter. Each walking session will end with a 3-5 min cool-down followed by 5 min of large muscle flexibility exercise. At least two HR readings (by HR monitors) will be taken during each supervised walking session to monitor compliance to the prescribed intensity. Speed and grade will be adjusted individually to insure that participants exercise at their prescribed exercise intensity.

The exercise prescription for the home-based sessions will allow the participant to perform over ground walking, or treadmill walking, elliptical or stationary bike if available. They will be counseled to exercise at a moderate-intensity as determined by a rating of 13-15 using Borg's Rating of Perceived Exertion.⁷⁶

Throughout the 18 month intervention period, those in the EX treatment arms will also wear a Fitbit device that will be integrated with the study website. Here, participants will view receive daily feedback relative to sustained bouts of physical activity (i.e., greater than 10 consecutive minutes of movement). As in the SitLess intervention, participants begin wearing the Fitbit daily for the first 9 months and then wear time is tailored to each individual for the remainder of the study, however, we ask that participants use the devices at least 2 days each week.

9-mo Follow-up phase—During this phase, participants will receive a monthly phone call or email contact for the purpose of emphasizing adherence to their moderate-intensity exercise goal of 5-6 days/week to maintain a volume of 200 min/week.

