The nature, purpose, and risks of all tests will be explained to participants prior to obtaining their written consent and prior to each test. All examiners will be blinded to participant treatment assignment and are trained in the standardized conduct of all tests. Standardized written instructions will be provided.

Study Measure(s)

1. Baseline demographic data will be recorded based on participant self-report. Medical information on prior and existing co-morbidities and hospitalizations will be ascertained by self-report and confirmed by direct query of the participant at the screening visit. We will also record medication use by asking participants to bring in all medications (including nutritional supplements).
2. Adverse events will be assessed by asking participants at each assessment visit, and during monthly phone or email contact with participants during the 9-month follow-up phase, to report any health changes, injuries, etc. and these will be recorded using the Adverse Event Form.
3. Body weight and composition: Body weight (the study's Primary Outcome) will be measured in our clinic on the same scale. Body composition, bone density, visceral fat will be measured by dual-energy X-ray absorptiometry (DXA; Hologic Discovery W, Bedford, MA). All scans will be performed and analyzed by our trained DXA technician who is certified by the International Society for Clinical Densitometry. Bone mineral density (BMD) will be measured using specific scans of the anterior-posterior spine (L1-L4) and proximal femur. Visceral fat area will be measured from the whole-body scan in a 5-cm wide region across the entire abdomen just above the iliac crest at a level approximate with the 4th lumbar vertebrae.⁷⁷
4. Resting metabolic rate will be assessed to determine participant's weight-maintaining energy needs for prescribing the 400 kcal/d energy deficit for WL and will be measured again at 6- and 18-months to determine its response to the interventions. RMR will be measured in the morning after an overnight fast (8 hour minimum of no food, beverage, alcohol, caffeine or strenuous exercise) by indirect calorimetry.⁴¹ Upon arrival, subjects are asked to lie quietly for 20-30 min before testing. Measurement of oxygen consumption and carbon dioxide production are collected continuously for at least 30 min and RMR is calculated using the Weir equation.⁷⁸

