7. Psychosocial Assessments: Since attachment-related behavior is an important facet of group-mediated interventions and known to be associated with responsiveness to behavior change, we will assess anxiety and avoidance experienced in close relationships.⁹¹ As social cognitive measures, we will assess self-efficacy expectations related to physical activity⁹² and eating behavior,⁹³ and outcome expectations for physical function and appearance.⁹⁴ Perceived stress will be evaluated with a short-form of the perceived stress scale,⁹⁵ trait mindfulness with the MAAS,⁹⁶ and control in resisting food using the power of food scale.⁹⁷

8. Craving Assessment: One tertiary goal of EMPOWER is to examine whether appetite and craving for desired foods may change over the course of the study. At baseline and follow-up visits, and following an overnight fast, we will administer a multidimensional state measure of craving.⁹⁸ The measure of craving provides subscales that assess the desire to consume highly valued foods, the positive reinforcement resulting from their consumption, the relief from negative feeling states that these foods provide, lack of control related to food consumption, and hunger.

9. Cardiometabolic risk factors: A fasting venous blood sample will be collected at baseline, 6-months and 18-months to measure lipoprotein lipids, C-reactive protein, and HbA1c, glucose and insulin (all will be measured by LabCorp). Vitamin D will only be collected at baseline. For those participants that agree to blood storage, plasma and serum will also be extracted from whole blood samples and stored at -80°C for future assays. We will also assess treatment effects on seated blood pressure, which will be assessed in the right arm using an automated sphygmomanometer after resting quietly for 10-15 minutes

10. Fatigue measures: The following fatigue questionnaires will be administered: 1) PROMIS Short-form 8a; 2) FACIT Fatigue Scale; and 3) Pittsburgh Fatigability Scale.

11. Cognitive function will be assessed during screening using the Montreal Cognitive Assessment (MoCA); participants must score ≥22 to be eligible. We will also assess psychomotor speed, attention, and working memory using the Digit Symbol Substitution Test (DSST). Participants are given a series of numbered symbols and then asked to draw the appropriate symbols below a list of random numbers. The score is the number of correctly made matches in 2 minutes (120 seconds).

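### The 8-hour pre-test exercise rule covers only RMR and only strenuous exercise, so after-effects of the last session cannot be separated from sustained effects in contrasts with WL+SitLess

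*Combined protocol and SAP*

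**What the plan says.** **RMR.** Study Measure(s), item 4, asks for a morning test after an overnight fast, defined as "8 hour minimum of no food, beverage, alcohol, caffeine or strenuous exercise". RMR is an outcome as well as a prescribing tool: it "will be measured again at 6- and 18-months to determine its response to the interventions".

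**Bloods and blood pressure.** Item 9 reads "A fasting venous blood sample will be collected at baseline, 6-months and 18-months to measure lipoprotein lipids, C-reactive protein, and HbA1c, glucose and insulin". It states no exercise condition. Blood pressure is taken after 10-15 minutes of seated rest, again with no exercise condition. The one definition of a fast for a clinic visit, under Participant screening and randomization, is "refraining from food, beverages (with the exception of water), alcohol and caffeine". Exercise is not listed.

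**Exercise prescription.** In the weight-loss phase, WL+EX and WL+EX+SitLess are asked for aerobic exercise "of moderate-intensity for 4-5 days/week, progressing to a duration of 200" minutes per week. Supervised sessions build to "40-50 min at 65-70% HRR by the end of the 6th week and thereafter". In follow-up the contacts reinforce a "moderate-intensity exercise goal of 5-6 days/week to maintain a volume of 200 min/week". WL+SitLess has no structured sessions.

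**Analysis.** Under Secondary analyses, initial models for the Aim 3 outcomes adjust only for gender and the baseline value. No field or model term for time since the last session is described.

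**The concern.** The RMR rule shows that the protocol itself regards recent exercise as a disturbance to a resting measurement. As worded, it may not reach the exercise the trial prescribes. The sessions are labelled moderate, so a literal reader could conclude that they are not *strenuous*. Even a reader who counts them as strenuous would allow a session the evening before, because 8 hours before a morning test reaches back only to the night.

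The exposure differs by arm and by time. Regular exercisers are excluded at entry, so few baseline values should follow a training session. At 6 and 18 months two arms are exercising on most days and the third is not. Baseline adjustment cannot remove a difference that arises only at follow-up.

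Aim 3 predicts that WL+EX+SitLess improves outcomes, including cardiometabolic risk, more than either other arm. Against WL+SitLess, a favourable but short-lived after-effect would push the result in the predicted direction and could be read as a sustained benefit. RMR, which the visit schedule lists among the secondary outcomes, has the same difficulty.

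**Working it through.** The plan gives no figure on this point, so there is none to reproduce. The check has two parts: how often the exposure can occur, and what it would do under assumed effect sizes.

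**1. Exposure**

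Inputs: 4-5 sessions a week at 6 months and 5-6 at 18 months (Aerobic exercise intervention). Assumptions: full adherence, one session per exercise day, and a visit day unrelated to the exercise schedule.

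Chance of a session on the day before, with *k* exercise days a week: *k*/7.
Chance of a session within the two days before: 1 − C(5,*k*)/C(7,*k*).

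| *k* | Applies at | Day before | Within two days |
|---|---|---|---|
| 4 | 6 months | 4/7 = 57% | 1 − 5/35 = 86% |
| 5 | 6 and 18 months | 5/7 = 71% | 1 − 1/21 = 95% |
| 6 | 18 months | 6/7 = 86% | 100% |

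WL+SitLess has no prescribed sessions, so its prescribed exposure is zero.

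**2. Effect on a comparison with WL+SitLess**

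Inputs: 51 completers per group (60 × 0.85, Sample size) and a two-sided 0.05 test (Aim 3, Secondary analyses). Assumption: a session the day before shifts the value by δ residual SD, and there is no lasting effect. The δ values are illustrative and do not come from the documents.

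Shift in the contrast = *f*δ, where *f* is the day-before share.
Standard error in residual SD units = √(2/51) = 0.198.
With *s* = *f*δ/0.198, rejection rate = 1 − Φ(1.96 − *s*) + Φ(−1.96 − *s*).

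Worked case: *f* = 4/7 and δ = 0.25 give a shift of 0.143 and *s* = 0.72. The rejection rate is 11.1%.

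| δ | Shift, *f* = 4/7 to 6/7 | False-positive rate |
|---|---|---|
| 0.10 | 0.06-0.09 | 6-7% |
| 0.25 | 0.14-0.21 | 11-19% |
| 0.50 | 0.29-0.43 | 30-58% |

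For scale, 51 per group has 80% power to detect (1.96 + 0.84) × 0.198 = 0.55 residual SD. The calculation ignores the extra variance from mixing exposed and unexposed participants within an exercise arm. That variance is *f*(1 − *f*)δ², at most (4/7)(3/7)(0.50²) = 0.06 of the residual variance, which is small.

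**3. Which comparisons are affected**

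WL+EX+SitLess and WL+EX share the same exercise prescription, so any after-effect largely cancels between them unless adherence differs. For Aim 3 the exposed contrast is WL+EX+SitLess against WL+SitLess. HbA1c is a longer-term marker and is left out. Body weight at 18 months, the primary outcome, is not addressed by this argument.

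**The case against.** **No after-effect is documented.** Nothing in the protocol states the direction, size or duration of a next-morning effect. The blood glucose checks around sessions, under Intervention risks, concern users of insulin or short-acting secretagogues and the time just before and after exercise. This stands. A reader might infer that the 6- and 18-month results are biased, or that a difference from WL+SitLess would be spurious. The documents do not support that; they support only that the two components cannot be separated.

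**The ongoing state may be the treatment effect.** Exercise is still prescribed at month 18, and Aim 3 speaks simply of treatment effects. That reading is legitimate. However, the RMR rule shows an intention to measure away from recent exercise. Without a fixed or recorded interval, results also depend on when visits happen to fall, whichever effect is wanted.

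**The exposure figures are a ceiling.** The Background says older adults are likely less able to keep to high exercise volumes, and months 10-18 are self-managed. Session times are not given. This stands, so actual exposure may be lower.

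**The asymmetry is not complete.** Entry criteria allow aerobic exercise up to 20 minutes a day, and a graded exercise test is done at screening, so baseline is not strictly exercise-free. WL+SitLess participants are asked for daily light activity, though not for structured sessions.

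**A rule may exist elsewhere.** Written test instructions are promised without their content, and the visit table was not readable in the copy reviewed. If bloods share the RMR morning, they would inherit the RMR rule, but that is still 8 hours and still limited to strenuous exercise.

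**Timing might be reconstructed.** Session logs, home-exercise records, Fitbit and ActivPAL data could help. In follow-up the Fitbit may be worn on as few as two days a week, so reconstruction would be partial.

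**Conclusion.** The point holds as a gap in measurement conditions, not as demonstrated bias. It applies to RMR, glucose, insulin, lipids, CRP and blood pressure at 6 and 18 months, in contrasts of an exercise arm with WL+SitLess. A reader might extend it to every follow-up value and every comparison. That goes too far, because HbA1c and the WL+EX+SitLess versus WL+EX contrast are largely unaffected and the primary outcome is not at issue.

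The exposure shares rest on full adherence and unrelated visit days. The consequence depends on an after-effect that the documents do not quantify: it is negligible at 0.10 residual SD, material at 0.25 and serious at 0.50. Because the planned analysis has no means of telling these cases apart and the remedy is cheap, the change should be made.

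**What to change.** For the RMR, fasting blood and blood pressure visits, in all arms, replace the 8-hour wording with one measurement condition: no structured exercise session, of any intensity, in the preceding 24 hours. Schedule the visit after a rest day that the participant already has. The prescription leaves 7 − 5 = 2 to 7 − 4 = 3 such days a week at 6 months, and 7 − 6 = 1 to 7 − 5 = 2 at 18 months. Weekly exercise volume and the 7-day ActivPAL totals are then unchanged. A 48-hour condition is not advised: with evening sessions it needs two consecutive free days, which a 6-day week does not have.

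Have staff who do no assessments record the date and time of the last session, so that examiners stay blinded. Add a sensitivity analysis that excludes values missing the interval.

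The cost is a change to the visit instructions, one extra data field and slightly tighter visit scheduling.

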		
–Serious conduction disorder, new Q waves or ST-segment depression (>3 mm), or uncontrolled arrhythmia
 
–Room air SpO₂ (oxygen saturation) at rest or with exercise qualifying for supplementary oxygen (SpO₂≤88%)
 
–Abnormal kidney or liver function (2x upper limit of normal);
 
–eGFR <45 mL/min/1.73m²
 
–Anemia (Hb<13 g/dL in men/ <12 g/dL in women);
 
– Uncontrolled diabetes (fasting glucose >140 mg/dl);
 
–Deficient levels of vitamin D (25 hydroxyvitamin D level < 20 ng/mL) in those not taking a vitamin D supplement;
 
–Smoker (No nicotine in past yr)
 
–No heavy alcohol use (>14 drinks/week)
 
–Unstable severe depression
	
Resting ECG
 
Self-report
 
Metabolic panel/CB screening blood test
 
Self-report
 
CES-D

Medication use		Regular use of: growth hormones, oral steroids, weight loss medications* or prescription osteoporosis medications*	Self-report and medication inventory
Research participation	Willing to provide informed consent; Agree to all study procedures and assessments; Able to provide own transportation to study visits and intervention	Current participation in other research study	Self-report

*Orlistat (Xenical), Belviq, Contrave, Saxenda, Phentermine (Adipex/Suprenza), Qsymia

**Fosamax (Alendronate), Miacalcin (Calcitonin), Boniva (Ibandronate Sodium), Evista (Raloxifene), Actonel (Atelvia/Risedronate), Forteo (Teriparatide), Reclast (Zoledronic Acid) (Zometa), Prolia (Denosumab/Xgeva, Protelos (Strontium Ranelate)

Those who pass phone screening will be scheduled for an in-clinic screening visit which is conducted in the early morning following an overnight (at least 8 hrs) fast which includes

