Hypotheses of our Aim 3 secondary outcomes will be tested at the 0.05 significance level using ANCOVA techniques similar to those used for the primary hypothesis. All initial models will be adjusted only for gender and baseline variable value; however, specific factors (e.g., age, race, initial body weight or composition, medication or supplement use, etc.) that may influence the measured responses to the interventions will be evaluated and possibly included in secondary analyses. We expect the treatments to similarly affect responses in men and women and between races. Nevertheless, we will assess whether there is an interaction between gender and/or race and treatment group, and will report this as part of our secondary results. We will also consider conducting analyses adjusted for intervention compliance and process measures (such as average attendance at the exercise sessions, amount of initial weight lost, social cognitive/group process measures, etc.) to examine the extent to which these factors moderate/alter the effect of the intervention on the outcomes.

Human Subjects Protection

Subject Recruitment Methods: We will recruit individuals using community-based recruitment strategies including newspaper ads and mass mailings. We will also advertise in the Aging Center's VITAL newsletter and participate in community outreach events.

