Finally, if any participant experiences a bone density decline (either at hip or spine) of $\geq 10\%$, or has a t-score of < -2.5 , at the 6-month DXA assessment, she/he will be counseled to stop their caloric restriction and will be referred to his/her primary care physician.

2) The risks of the structured exercise intervention may include: 1) musculoskeletal complications and muscle soreness in the early phases of the intervention, 2) an increased fall risk, and 3) increased risk of hypoglycemia or hyperglycemia, especially in participants with type II diabetes on insulin or short-acting insulin secretagogues.

Musculoskeletal and fall risks are minimized since all center-based exercise sessions will be supervised by trained exercise staff who will instruct participants in proper treadmill walking and balance safety, proper footwear, and in selection of safe walking areas outside of the center.

Hypoglycemia/hyperglycemia risks will be mitigated by following the recommendations of the American College of Sports Medicine and American Diabetes Association for safety precautions of exercise in patients with diabetes.⁹⁹ Specifically, risks will be reduced by educating participants of this risk, by discussing signs and symptoms for them to be aware of prior to, during, and after an exercise bout, and by encouraging proper nutrition and hydration prior to exercise. For center-based sessions, we will have easily digestible snacks, glucose tablets, and juice in the exercise center and we will encourage them to have one of these carbohydrate sources accessible during their home-based sessions. Participants who use insulin or short-acting insulin secretagogues for blood glucose control will have their blood glucose checked via glucometer before and after exercise at the supervised sessions and will be encouraged to do this for their home-based exercise. If a participant's glucose is <100 mg/dl we will require them to consume a snack containing about 15 grams of carbohydrate prior to exercise; if it is >300 mg/dL they will be encouraged to hydrate and postpone exercise until their blood glucose level is below 300 mg/dL. We will also encourage participants to monitor their glucose after exercise to determine if food consumption or medication changes should be made. In some cases, we may ask a participant to consult with their physician about reducing medication dosage prior to an exercise session.

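### Insulin users can enrol, but fasting insulin is analysed in all participants with no rule for values that may include injected insulin

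*Combined protocol and SAP*

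**What the plan says.** **Who can enrol.** In the inclusion/exclusion table, the only diabetes exclusion is "Uncontrolled diabetes (fasting glucose >140 mg/dl". The medication row excludes "Regular use of: growth hormones, oral steroids, weight loss medications* or prescription osteoporosis medications"; neither insulin nor any other glucose-lowering drug is listed. Under Intervention risks, item 2, the protocol expects such participants: "Participants who use insulin or short-acting insulin secretagogues for blood glucose control will have their blood glucose checked via glucometer before and after exercise".

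**What is measured.** Item 9 of Study Measure(s) lists the assays: "measure lipoprotein lipids, C-reactive protein, and HbA1c, glucose and insulin (all will be measured by LabCorp". Sampling is at baseline, 6 and 18 months. Cardiometabolic risk belongs to Aim 3, whose hypothesis compares WL+EX+SitLess with each of the other two arms.

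**How it is analysed.** Data analyses specifies intention to treat in everyone randomized. For Aim 3, tested at 0.05, "All initial models will be adjusted only for gender and baseline variable value". Medication or supplement use appears only among factors that may be considered for secondary analyses; whether baseline or follow-up use is meant is not stated. No rule covers fasting insulin in insulin users.

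**The concern.** Fasting insulin is useful as a risk marker because it reflects the participant's own secretion in response to insulin resistance. In someone who injects insulin, the assay may also register the injected product, to an extent that depends on product, assay, dose and timing. The value then means something different from the value in a non-user.

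Two things follow. The all-participant contrast mixes two quantities. A few large, variable values can also inflate the residual variance of a comparison with about 51 completers per arm.

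The medication covariate that the plan allows for does not solve this. A baseline-use indicator can shift users' mean, but it cannot make their values measure resistance and leaves their extra variance in the model. Adjusting for follow-up medication would condition on something that treatment may have changed.

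**Working it through.** **1. The plan's own power figure.** The documents give none for insulin, so the framework is checked on weight (Table 5: SD 8.2 kg, r = 0.87, 51 per group, alpha 0.025). Residual SD = 8.2 × √(1 − 0.87²) = 4.04 kg. SE = 4.04 × √(2/51) = 0.80 kg. Power for 2.7 kg = Φ(2.7/0.80 − 2.24) = 0.87, as stated.

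For Aim 3 the detectable effect at 80% power and alpha 0.05 is (1.96 + 0.84) × √(2/51) × √(1 − r²) = 0.555 × √(1 − r²). The stated 0.24 to 0.49 SD corresponds to r of about 0.90 to 0.47.

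**2. Simple noise model.** Assume a share p of participants use insulin and their residual SD is k times that of non-users. Residual variance is multiplied by 1 + p(k² − 1). A contrast planned at 80% power then has Φ(2.80/√(1 + p(k² − 1)) − 1.96). Leaving users out gives Φ(2.80 × √(1 − p) − 1.96).

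| Users (p) | Variance factor, k = 3 | Power, all | Power, non-users only |
|---|---|---|---|
| 2% | 1.16 | 0.74 | 0.79 |
| 5% | 1.40 | 0.66 | 0.78 |
| 10% | 1.80 | 0.55 | 0.76 |
| 15% | 2.20 | 0.47 | 0.73 |

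At 5% users, power with everyone included is about 0.74 for k = 2 and 0.47 for k = 5.

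**3. Simulation on the assay scale.** All inputs except 51 per arm are assumptions:
- Endogenous fasting insulin is log-normal with median 13, log SD 0.5 and pre-post correlation 0.7.
- One arm has a true 20% reduction in the endogenous component.
- Users carry a uniform excess at each visit, in the same units.
- The test is two-sided ANCOVA on baseline at 0.05, without sex, in 8,000 replicates (Monte Carlo error about 0.006 at most).

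| Analysis and users' excess | 3% users | 6% | 10% |
|---|---|---|---|
| Raw, all; 10–100, redrawn each visit | 0.54 | 0.38 | 0.27 |
| Raw, all; 10–100, follow-up within ±20% of baseline | 0.72 | 0.69 | 0.64 |
| Raw, all; 5–30, redrawn | 0.76 | 0.73 | 0.67 |
| Raw, non-users only | 0.80 | 0.79 | 0.76 |
| Log, all; 10–100, redrawn | 0.83 | 0.78 | 0.73 |
| Log, all; 10–100, within ±20% | 0.85 | 0.84 | 0.81 |
| Log, all; 5–30, redrawn | 0.85 | 0.84 | 0.81 |
| Log, non-users only | 0.87 | 0.86 | 0.84 |

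Compared within the same run, the log-scale loss from including users is 0.01 to 0.11. Restriction did not lose power in any scenario.

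**4. Glucose and HbA1c.** Suppose dose reductions occur only in exercise arms. The expected shift against WL+SitLess is user share × share reducing × shift in SD:
- 5% × 50% × 2 SD = 0.05 SD
- 10% × 50% × 2 SD = 0.10 SD
- extreme: 15% × 100% × 4 SD = 0.60 SD

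The stated detectable effects are 0.24 to 0.49 SD. For WL+EX+SitLess against WL+EX the expected shift from the exercise-session prompt is about zero, because both arms exercise.

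**The case against.** **The size is driven by assumptions.** This stands. The lowest raw-scale figures need a large excess that is unrelated between visits, and nothing in the documents supports that pattern over a smaller or steadier one. Scale matters about as much: log-scale power with everyone included (0.83, 0.78, 0.73 in the worst case) is close to raw-scale power in non-users (0.80, 0.79, 0.76). The main argument for restriction is therefore what the measurement means; power is secondary.

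**The plan partly covers it.** The glucose exclusion and Medical Director approval limit who enters. Database management includes range checks and outlier review, and medication use may be considered as a factor. These would flag odd values, but none says what to do with a verified value from an insulin user.

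**A stronger reading.** A reader might infer that all glycaemic contrasts are confounded by arm, because medication changes are linked to exercise sessions and "Participants in the WL+EX and WL+EX+SitLess treatment arms will be asked to perform structured aerobic exercise". The documents do not support this:
- The sentence is conditional: "In some cases, we may ask a participant to consult with their physician about reducing medication dosage prior to an exercise session". It describes a possible referral and does not establish routine or lasting dose reduction.
- A dose change comes after randomization, so it is an intercurrent event. The as-randomized contrast still validly estimates the total effect of assignment; it just cannot be read as an effect at constant medication.
- Any asymmetry concerns only contrasts with WL+SitLess. Even there, all arms follow the same diet, so weight loss could lead to medication changes in every arm.
- Centre-based sessions are described only for months 1 to 9, well before the 18-month sample.

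**Conclusion.** The point holds for fasting insulin. Insulin users are eligible, their values may not measure what the outcome is meant to measure, and the plan has no rule for them. At assumed user shares of 3% to 10%, raw-scale power for a 20% reduction is 0.27 to 0.76 with users included and 0.76 to 0.80 without. On the log scale the loss is about 0.01 to 0.11. These ranges rest on assumed user shares and on an assumed size and stability of the injected component, so they illustrate the problem and do not predict it. If few or no insulin users enrolled, the effect is negligible.

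For glucose and HbA1c the all-participant analysis is sound as an effect of assignment. The illustrative shift of 0.05 to 0.10 SD is small beside the detectable effects and justifies only an optional sensitivity analysis. The issue is confined to Aim 3, chiefly to one analyte; the primary weight comparison is untouched.

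**What to change.** **Main change (SAP wording).** Prespecify that fasting insulin, and any index derived from it, is analysed on the log scale in participants not using insulin at baseline, with the all-participant analysis as a sensitivity analysis. Report the number of baseline insulin users by arm. Baseline use precedes randomization, so the restricted comparison is still a randomized one.

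**Optional, lower priority.** For glucose and HbA1c, keep the as-randomized analysis and state that it estimates the total effect of assignment. Add a sensitivity analysis in participants not on insulin or secretagogues at baseline. Report changes in glucose-lowering treatment by arm at 6 and 18 months if those data exist. Study Measure(s), item 1, describes medication recording with the baseline data, and the visit schedule table is not in the available text, so follow-up recording can be neither assumed nor ruled out.

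**Cost.** The main change needs no new data, since medications are already inventoried. The restricted result applies only to non-users and loses a few participants: at 10% users, about 5 of 51 per arm (0.10 × 51 = 5.1). If medications are not recorded at follow-up, reporting treatment changes would need extra data collection.
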